12.2 Screening/Baseline Assessments

Screening and baseline assessments will be conducted as shown in **Table 1**. Screening and baseline assessments may be performed concurrently. A single blood draw for genetic samples will be performed during the screening period for those subjects who consented to the genetics part of the study. This one draw will result in the collection of one tube of blood for genomic DNA analysis and two tubes of blood for RNA analysis. Two additional tubes of blood will be collected for baseline plasma bupropion and BDNF levels determination during screening. The blood for genomic DNA analysis will also provide data to be used in conjunction with genetic analysis of methamphetamine dependence, even if the subject is ultimately found ineligible to participate in the main study. Data that will be used in the genomic analyses include: demographic data, medical and substance use history (timeline followback, quantity frequency interview, methamphetamine urine levels), family history, and diagnostic information obtained by the MINI. Detailed information about what data will be used in the genetic part of the study is enumerated in a separate Genetics Informed Consent Form.

Screening/baseline assessments will occur over a consecutive 14-28 day period. A potential subject must complete the minimum set of baseline measures over a consecutive 14-day period to be eligible for the study. If a subject fails to satisfy eligibility criteria during the screening and baseline periods, s/he may be re-screened. This decision will be made on a case-by-case basis.

Baseline measures over the consecutive 14-day period include collection of at least four urine specimens prior to randomization and the accompanying other baseline repeated measures. Demographic data and the reason that any subject did not meet eligibility criteria must be recorded for anyone who consented to screening even if the individual is a screening failure.

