13.1 SCREENING ASSESSMENTS

Prior to randomization into the study, subjects will be screened to determine if they meet eligibility requirements. In addition, certain baseline assessments that are part of eligibility determinations will also provide physiological, psychological, and disease status information prior to investigational product administration. Screening and baseline assessments may be performed concurrently; however, baseline assessments will include only those acquired during a 14-day consecutive period prior to randomization. An End of Trial eCRF must be completed if a subject fails to meet eligibility requirements or discontinues screening before eligibility is established.

- 1. Informed consent
- 2. Locator form
- 3. Demographics
- 4. Timeline follow-back for methamphetamine use in the prior 30 days
- 5. Quantity frequency interview
- 6. Psychiatric evaluation and MINI evaluation for DSM-IV diagnosis of methamphetamine dependence and Axis-I disorders
- 7. Adult ADHD interview (ACDS)
- 8. Medical history and Family History Questionnaire
- 9. Prior medications for the 30 days prior to informed consent
- 10. Infectious disease serology/Syphilis test
- 11. Alcohol breathalyzer
- 12. Physical exam
- 13. Vital signs
- 14. Hematology and blood chemistries
- 15. Blood for DNA analysis (for all subjects who consent to genetics part of study)
- 16. Blood for RNA analysis (for all subjects who consent to genetics part of study)
- 17. Blood for plasma BDNF levels (for all subjects)

- 18. Blood for baseline plasma bupropion levels (for all subjects but will only be analyzed for subjects who are randomized onto the study
- 19. Medical Urinalysis
- 20. Pregnancy Test
- 21. ECG
- 22. AEs at each visit
- 23. Concomitant medication use at each visit
- 24. ASI-Lite
- 25. HAM-D (performed weekly during screening/baseline period)
- 26. Urine drug screen onsite test device (3 times per week)
- 27. Urine Methamphetamine/Creatinine for Central Lab (3 times per week) Note: Assay for methamphetamine and creatinine as well as the urine toxicology screen will be performed only for urine samples collected from the subjects who are randomized into the study.
- 28. SUR (3 times per week)
- 29. CBT Compliance (two 60-minute sessions weekly, to be checked at every visit and verified with the CBT attendance log)
- 30. Eligibility Checklist (initial evaluation)

		Tab	le 1.	Over	view	of S	tudy A	sses	smer	nts								

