Assessment Study Week	Screening -4 to -1	Baseline	Intervention Phase Follow-up															
		-2 to -1	1	2	3	4	5	6	7	8	9	10	11	12/ Term	13	14	15	16
Screening																		
Informed consent	Х																	
Locator Form	Х																	
Demographics	Х																	
Timeline follow-back (30 days)	Х																	
Quantity Frequency Interview	Х																	
MINI	Х																	
ACDS	Х																	
Medical and family ^a history	Х																	
Prior medications	Х																	
Infectious disease panel/RPR	Х																	
Alcohol breathalyzer ^b	Х	3 X/week	3X	3X	3X	3X	3X	3X	3X	3X	3X	3X	3X	3X	Х	Х	Х	Х
Safety																		
Physical exam	Х													X ^l				
Vital signs	Х		Х	Х	Х	Х	Х	Х	Х	Х	Х	Х	Х	Xl				
Hematology	Х													X ^l				
Blood chemistries	Х													Xl				
Medical urinalysis	Х													Xl				
Pregnancy test ^c	Х		Х			Х				Х				X ^l				
ECG	Х													X ^l				
Adverse events ^d	3X/week	3X/week	3X	3X	3X	3X	3X	3X	3X	3X	3X	3X	3X	3X	Х	Х	Х	Х
Concomitant medications ^d	3X/week	3X/week	3X	3X	3X	3X	3X	3X	3X	3X	3X	3X	3X	3X	Х	Х	Х	Х
Eligibility Checklist ^e	Х	Х																
Efficacy																		
ASI-Lite ^f	Х	Х												X				
AISRS		Х				Х				Х				X				
HAM-D	weekly	weekly		Х		Х		Х		Х		Х		X ^l				
BSCS		weekly	Х	Х	Х	Х	Х	Х	Х	Х	Х	Х	Х	X ¹			1	
CGI-S		weekly	Х	X	X	X	X	Х	Х	Х	Х	Х	Х	X ¹			1	
CGI-O		weekly	Х	Х	Х	Х	Х	Х	Х	Х	Х	Х	Х	X ^l				
HRBS		X	l	l	İ	1		İ –	1	1		İ –	1	X ^l	1	1	l	1
SUR	3X/week	3X/week	3X	3X	3X	3X	3X	3X	3X	3X	3X	3X	3X	3X	Х	Х	Х	Х
Urine methamphetamine/	3X/week	3X/week	3X	3X	3X	3X	3X	3X	3X	3X	3X	3X	3X	3X	х	х	x	X
creatinine ^g																		

Table 1. Overview of Study Assessments																			
Assessment	Screening	Baseline	Intervention Phase													Follow-up			
Study Week	-4 to -1	-2 to -1	1	2	3	4	5	6	7	8	9	10	11	12/ Term	13	14	15	16	
Urine bupropion/hydroxybupropion ⁿ			3X	3X	3X	3X	3X	3X	3X	3X	3X	3X	3X	3X					
Blood for DNA (genetics consent)	Х																		
Blood for RNA ^h (genetics consent)	Х							Х						X ¹					
Bupropion Plasma Levels ⁱ	Х							Х						X ¹					
BDNF Plasma Levels	Х							Х						X ¹					
Urine drug screen – onsite test device	3X/week	3X/week																	
CBT compliance	X ^k	X ^k	3X	3X	3X	3X	3X	3X	3X	3X	3X	3X	3X	3X	X ^m	X ^m	X ^m	X ^m	
Investigational Product compliance ^j			Х	х	Х	Х	Х	X	х	Х	Х	Х	Х	x ¹					
End of Trial form	X – if screen fail																	Х	
Follow-up questionnaire																		Х	

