^a The family history questionnaire will only be done on subjects who consent to the genetics testing even if they are considered a screen failure for the bupropion/methamphetamine study.

^b An alcohol breathalyzer test will be performed in accordance with institutional policy and state law.

^c The pregnancy test on Day 1 must be performed prior to randomization and administration of the first dose of investigational product.

^d These assessments are performed after the first screening visit

^e Eligibility is checked during screening and at baseline visits as data become available such that if a subject does not meet inclusion or exclusion criteria, the subject is no longer screened.

^f The ASI-Lite will be performed during screening; however, if the entire screening/baseline period takes longer than 14 days, the ASI must be repeated such that the it is collected during baseline.

^g Assay for methamphetamine and creatinine as well as the urine toxicology screen will be performed only for urine samples collected from the subjects who are randomized into the study.

^h Blood for RNA analysis should be collected at the same time of day at every collection time point to control for circadian rhythm effects on expression. One RNA tube will be collected during screening/baseline and at all other time points during the intervention phase of the study.

ⁱ During the intervention phase, blood for bupropion levels will be taken before the daily dose.

^j Investigational product compliance is reviewed at every clinic visit with the subject by self report but the pill count is only done weekly.

^k Two 60 minute early recovery skills group sessions given weekly until randomization occurs. Compliance should be checked at each visit and verified with the CBT attendance log.

¹ These assessments are performed at the last visit of Week 12 or at earlier termination.

^mCBT sessions are performed once a week during the follow-up period.

ⁿ Bupropion/hydroxybupropion will be analyzed after study closure only in those assigned to a bupropion treatment group as a surrogate marker for medication compliance.

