- Y. Proportion of subjects who met the criteria for being abstinent according to the primary outcome measure during Weeks 11 and 12 who continue to be abstinent Weeks 13 through 16 as determined by self-report and confirmation by methamphetamine negative urine sample.
- **Z.** Proportion of subjects who met the criteria for being abstinent according to the primary outcome measure who continue to be abstinent Weeks 13 through 16 as determined by self-report alone.

The proportions will be calculated using the number of subjects who meet the criteria for continued abstinence as described above by the number who were abstinent during weeks 11 and 12 as defined by the primary outcome measure.

Plasma Levels of Bupropion and BDNF

Bupropion is primarily metabolized in human liver by CYP 2B6, an isoform that shows high interindividual variability in expression and catalysis which has been hypothesized to account for the variability in treatment response and toxicity associated with bupropion. Rapid clearance of bupropion via hydroxylation could account for treatment failure, likewise, slow clearance could account for toxicity. Recently, the 6B haplotype of CYP 2B6 has been shown to be a significant predictor of bupropion hydroxylation in human liver microsomal preparations, thus suggesting that individuals with this haplotype may be poorer responders to treatment. At steady state, the mean C_{max} following a 150-mg dose of bupropion every 12 hours is 136 ng/mL. Bupropion plasma levels will be examined for correlation to CYP 2B6 haplotypes and to treatment success.

Elevated plasma BDNF levels are associated with methamphetamine neurotoxicity, and are known to decline during abstinence from methamphetamine. Since bupropion also has an independent effect on BDNF, plasma samples will be tested for bupropion level at the same timepoints as plasma for BDNF is obtained. This will allow the evaluation of whether BDNF is affected differently in subjects receiving bupropion compared to those receiving placebo, and whether this effect influences methamphetamine use or abstinence. In addition, it is also hypothesized that methamphetamine users who have the BDNF 66Val homozygote will be more likely to benefit from bupropion than those who do not.

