Microarray Data Analysis. All microarray data generated from Affymetric Human Genome U-133 Plus 2.0 array will be subjected to a series of steps for normalization and filtering, which includes log-transformation, normalization within a slide, scaling among slides, and data filtering. To reduce individual variation, we will use expression profile of each subject prior to administration of investigational products as the baseline. All expression profiles of that individual at other time points will be compared with the baseline. After appropriate normalization, various statistical approaches will be applied to select genes differentially expressed in the bupropion and placebo groups. Computer programs written in SAS, Fortran, or MatLab for the traditional *t*-test, the SAM method (a modified *t*-test), variance analysis under a mixed model, and a mixture-model approach have been implemented in our laboratory and are ready for handling the data generated from this project. Given that each method has its own features, and there is no clear standard or consensus as to which method is preferable, we plan to use all of these methods to analyze each dataset. Only those genes that can be identified repeatedly by different methods will be selected for further characterization.

After differentially expressed genes are identified, we plan to use various clustering techniques over different experimental groups to analyze the expression patterns. Expression profiles will be grouped by: a) hierarchical cluster analysis using CLUSTER and TREEVIEW (http://rana.stanford.edu/software/), b) quality clustering (http://www.genome.org/cgi); and c) self-organizing maps (http://www-genome.wi.mit.edu/). The outputs from each program will be compared with respect to the clusters formed. These data will be used to determine relationships between the clusters, disease status, and intervention group and response. These methods have been routinely used in our microarray data analysis.^{68,154-156}

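### The BDNF and RNA reference samples may be drawn up to 28 days before dosing, because no rule places them in the 14-day baseline window or has them repeated

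*Protocol*

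**What the plan says.** **Timing of the samples.** Section 12.2 puts the BDNF tube in screening: "Two additional tubes of blood will be collected for baseline plasma bupropion and BDNF levels determination during screening". It does the same for the DNA and RNA tubes, which come from one draw in people who agreed to the genetics component. On duration it says: "Screening/baseline assessments will occur over a consecutive 14-28 day period". Section 13.1 lists RNA and BDNF as screening items 16 and 17. In Table 1 the row "BDNF Plasma Levels" is marked under Screening (Weeks -4 to -1), not under Baseline (Weeks -2 to -1), and then at Weeks 6 and 12. The RNA row is marked alike. Neither sample is in the Section 13.2 list of baseline assessments.

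**What counts as baseline.** Section 13.1 says that "baseline assessments will include only those acquired during a 14-day consecutive period prior to randomization". Footnote f to Table 1 applies this to the ASI-Lite, which is also taken in screening: "if the entire screening/baseline period takes longer than 14 days, the ASI must be repeated".

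**Use of the samples.** Section 4.1.9 hypothesises that BDNF falls in subjects who reduce their use over the dosing period and does not change in those who do not, whichever arm they are in. Secondary objective 9 (Section 5.2) covers BDNF and clinical success. For expression, Section 15.4.4 says "we will use expression profile of each subject prior to administration of investigational products as the baseline".

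**The concern.** A tube drawn at the first screening visit of a four-week screening complies with Section 12.2 and Table 1, yet it is not a baseline value as Section 13.1 defines one. It remains the only pre-dose BDNF or RNA value for that subject.

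The interval it may span is not a quiet one. Section 11.2 offers two recovery-skills sessions a week from consent to randomisation, with the aim of helping people stop using. Section 15.2.2 says of the marker: "Elevated plasma BDNF levels are associated with methamphetamine neurotoxicity, and are known to decline during abstinence from methamphetamine". A subject who stops in Week -4 or -3 and stays stopped could show lower BDNF at Week 6 than at screening, although use did not change during dosing. Read against Section 4.1.9, that subject counts against the hypothesis for a reason of timing alone. The use-reduction outcomes D3 to D6 in Section 15.2.2 are referred to the 14-day baseline period, so use and BDNF may be measured from different starting points. Expression profiles have the same weakness, since each later profile is compared with this one sample.

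**Working it through.** The protocol gives no figure for this gap, so the check derives the largest gap that its schedule allows. The sample size in Section 15.5 concerns the primary outcome and does not enter.

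**Inputs**
- Screening/baseline lasts 14 to 28 days (12.2), so the longest lead from draw to first dose is L = 28 days. This takes the first dose to follow directly on randomisation; footnote c to Table 1 has both after the Day 1 pregnancy test.
- The baseline window is 14 days (13.1), so L is at most 14 if the draw is confined to it.
- On-treatment draws are at Weeks 6 and 12, preferably at the first visit of the week (13.3). Those visits are Day 36 and Day 78, so T = 35 and T = 77 days after the first dose.
- Recovery sessions run at two per week (11.2), so up to 2 × 4 = 8 fall within a 28-day lead.

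**Formula.** Pre-dose share of the interval = L / (L + T).

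| Lead L | Week 6 (T = 35) | Week 12 (T = 77) |
|---|---|---|
| 28 days (longest allowed now) | 28/63 = 44% | 28/105 = 27% |
| 14 days (longest inside the baseline window) | 14/49 = 29% | 14/91 = 15% |
| 1 day | 1/36 = 3% | 1/78 = 1% |

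Draws on the last day of the week change little. At L = 28, Day 42 gives 28/69 = 41% and Day 84 gives 28/111 = 25%.

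**Comparison with the ASI-Lite.** Both the ASI-Lite and these tubes are first taken in screening. Section 13.2 explains that the early ASI-Lite serves the genetics analysis of people who are not enrolled, and footnote f then secures a value inside the window for those with a longer screening. For the blood samples, Section 12.2 gives a reason to sample people later found ineligible only for genomic DNA, and nothing secures a later BDNF or RNA value.

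**The case against.** Most of the opposing case is sound, and it narrows the point.

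- **The early draw is allowed, not required.** Screening Weeks -4 to -1 contain Baseline Weeks -2 to -1, the two may run concurrently, and the whole period may be only 14 days. Footnote h describes the RNA tube as taken in screening/baseline. This stands: many draws may fall inside the window.
- **Plasma bupropion is not affected.** Exclusion criterion 14a bars bupropion use in the past 30 days, so the pre-dose value should be about nil whenever it is drawn, and no change from it is planned. This stands.
- **No bias between arms.** The draw precedes randomisation, so drift before dosing is expected to be equal in both arms. The Section 15.2.2 question, whether BDNF is affected differently on bupropion than on placebo, gains noise only. This stands.
- **BDNF change is not a lettered outcome.** The change reading comes from Section 4.1.9, and its computation may be left to an analysis plan that is not shown. This lowers the weight of the point. It does not remove it, because no analysis plan can supply a sample that was not taken.
- **Use could be aligned to the draw date.** Self-report and urine are collected three times a week throughout screening. That would make the BDNF-use association coherent, but over screening plus dosing, not over the dosing period that Section 4.1.9 names. It does nothing for the expression profiles.
- **The work is secondary.** Expression analysis depends on favourable efficacy (13.6.30), and BDNF is the last of nine secondary objectives. This stands, although BDNF blood is taken from all subjects and objective 9 itself carries no such condition.

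**Conclusion.** The point holds as a minor one. The protocol lets the sole BDNF and RNA reference sample fall up to 28 days before dosing, and so up to 14 days (28 - 14) before its own baseline window opens, without the repeat rule that it gives the ASI-Lite. Within-subject BDNF change (4.1.9, objective 9) and expression change (15.4.4) can therefore include change before treatment.

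The worst case is 44% of the interval to Week 6 and 27% of that to Week 12. It assumes a full 28-day screening, a draw at its start and on-treatment draws at the first visit of the week. These are shares of elapsed time. The protocol gives no rate of BDNF or expression drift, so the share of any observed change cannot be stated.

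A reader might go further and infer that these samples always lie outside the baseline window, that the treatment comparison is biased, or that up to 44% of a BDNF change is pre-treatment. The protocol supports none of these: the draw may fall inside the window, drift before randomisation does not favour either arm, and time is not effect. The primary outcome is untouched.

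**What to change.** **Preferred.** In Sections 12.2 and 13.2 and Table 1 (with items 16 and 17 of 13.1 to match), take the BDNF and RNA tubes at the last baseline visit or on Day 1 before dosing. Section 13.6.30 restricts the genetic draws to Monday to Wednesday for shipping, so the RNA visit must fall on one of those days. Keep the DNA tube at screening, where it also serves people later found ineligible. A draw one day before dosing cuts the pre-dose share to about 3% at Week 6 and 1% at Week 12; a few days' lead adds somewhat to this.

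**Partial alternative.** Extend footnote f so that BDNF and RNA are redrawn within the 14-day baseline when screening/baseline exceeds 14 days. This caps the share at 29% (Week 6) and 15% (Week 12), and it keeps the screening samples from screen failures.

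**Cost.** A text and table edit at visits that already exist, and at most one extra venepuncture for some randomised subjects. Under the preferred option no BDNF or RNA samples come from screen failures. The edit has to precede sampling, because a pre-dose sample that was not taken cannot be recovered later.

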12.3 Subject Randomization

Adaptive randomization using an interactive voice randomization system (IVRS) will be used to balance study intervention groups within each clinical site based on methamphetamine use (18 or less *versus* 19-29 days out of 30 days prior to signing consent), severity of depression symptoms (HAM-D score ≤ 12 *versus* >12), and presence of adult ADHD. The procedure allocates group assignment based on the assignments and prognostic variable levels for all previously randomized subjects. A new subject will be randomized with a "biased coin" procedure that uses randomization probabilities, favoring the treatment with the deficit enrollment, to improve the balance on group assignment.¹⁴³

When ready to randomize a subject, designated site staff will call the IVRS number and enter the information regarding each randomization variable presented above over the phone. These descriptors can then be used to randomize subjects into study intervention groups. Site staff enters relevant data using either the phone key pad or simple voice commands. The IVRS repeats the users' responses to verify entered data before saving and assigning an intervention group. The system allows the user to back up or re-enter data at any point prior to the intervention group assignment. The information is not finalized until the user reviews the entered data. Once the user has approved the information, the randomization algorithm is activated and an intervention group is assigned. All users are trained on the IVRS as part of the study training plan.

All randomization data are stored on the KAI network on a secure drive that is only accessible to a designated KAI network support staff member and the programmer responsible for programming the IVRS system. There is a physical firewall in place to prevent access to the KAI network via the Web. This limited access to randomization data is done to prevent inadvertent or unauthorized breaking of or tampering with the study blind.

12.4 Intervention Phase

At the first clinic visit, subjects will be given instructions on how to administer the investigative product, bupropion or placebo, and will be given a ten-day supply. This is a double-blind study in which neither the subject nor the site staff will know if the subject is receiving bupropion or placebo. The subject will be given the first dose of the investigational product in the clinic regardless of the time and will be observed for one hour to monitor for immediate adverse symptoms.

Subjects will be scheduled for CBT and assessment visits three times per week usually on a Monday, Wednesday, and Friday for 12 weeks. Two consecutive days may be scheduled around holidays or other schedule conflicts. Clinical evaluations are described in detail in Section 13.

